### **9.2.2 Neurofilament light chain**

NF-L levels in serum will be listed by treatment group and timepoint including changes from Baseline. Descriptive summaries will be presented by treatment group and timepoint for absolute values, changes from Baseline and percentage changes from Baseline.

Participant NF-L levels in serum will be plotted against planned time. Mean NF-L levels, mean change from Baseline and percentage change from Baseline will be plotted against planned time by treatment group.

## **9.3 Immunological analyses**

All analyses described in this section will be based on the SS.

### **9.3.1 Immunoglobulins**

Immunoglobulins (IgA, IgE and IgM) will be listed by treatment group and timepoint including changes from Baseline. Descriptive summaries will be presented by treatment group and timepoint for both absolute values and changes from Baseline.

Individual figures over time (absolute value) will be presented by participant, with all variables overlaid on the same plot and separate plots each participant.

Any values that are BLQ or ALQ will be handled as described in Section 4.2.4.

### 9.3.2 [REDACTED]

[REDACTED] will be measured using a three-tiered assay approach: screening assay, confirmatory assay and titration assay. The results for the [REDACTED] measurements will be listed by treatment group and timepoint based on the SS, including the Screening assay, confirmatory assay and titer (if applicable).

Samples will first be evaluated in the screening assay using a false positivity rate of 5% (reported as negative screen or positive screen), followed by analysis of screened positive samples in the confirmatory assay (which is a drug depletion assay) to confirm the true positivity of the samples (reported as negative immunodepletion or positive immunodepletion positive). Samples that are confirmed as positive will be evaluated in a titration assay to quantify the [REDACTED] level and will be reported as titer (reciprocal dilution factor including minimum required dilution (MRD)).

Screening, confirmatory and titer cut points of the respective assays will be determined by the bioanalytical laboratory.

The [REDACTED] sample status should be determined for each visit where samples were taken for [REDACTED] analysis:

- Sample values that are either negative screen or positive screen and negative immunodepletion will be defined as [REDACTED] negative
- Sample values that are positive screen and positive immunodepletion will be defined as [REDACTED] positive.

There will be six [REDACTED] participant status classifications

- (1) For participants who are negative at baseline, and antibody negative at all sampling points post treatment (including FV)- pre [REDACTED] negative- treatment induced [REDACTED] negative
- (2) For participants who are negative at baseline, and antibody positive at any sampling point post treatment (including FV)- pre [REDACTED] negative- treatment induced [REDACTED] positive. If a participant has a missing pre-treatment sample (either missing or insufficient volume) at baseline with one or more [REDACTED] positive post-treatment samples will be also classified as pre [REDACTED] negative- treatment induced [REDACTED] positive
- (3) For participants who are positive at baseline, and antibody negative at all sampling points post treatment (including FV)- pre [REDACTED] positive- treatment reduced [REDACTED]
- (4) For participants who are positive at baseline, and are positive at any sampling point post treatment (including FV) with titer values of the same magnitude as baseline (i.e.  $\leq$  then a predefined fold difference from the baseline value)- pre [REDACTED] positive - treatment unaffected [REDACTED]
- (5) For participants who are positive at baseline, and are positive at any sampling point post treatment (including FV) with increased titer values compared to baseline (above a predefined fold difference increase from baseline value which will be defined within the validation of the assay and will be included in the TFLs and/or SAP when available)- pre [REDACTED] positive- treatment boosted [REDACTED] positive.
- (6) For participants who have a positive pre-treatment sample and some post-treatment samples are missing, while other post-treatment samples are [REDACTED] negative, the participant will be classed as inconclusive.

- A participant will be classified as having treatment-induced [REDACTED] positivity when meeting one of the following criteria:
  1. The Baseline result is [REDACTED] negative and at least one post-Baseline timepoint is [REDACTED] positive
  2. The Baseline result is [REDACTED] positive and at least one post-Baseline measurement shows a pre-defined fold increase in titer from the Baseline value (the fold increase from Baseline required to meet this criterion will be defined with the development of the assay and will be included in the TFLs)

The available [REDACTED] sample results will be listed. The listing will include rozanolixizumab concentration, [REDACTED] sample result [REDACTED] negative or positive), together with the confirmatory result (% inhibition) and [REDACTED] titer for results that are [REDACTED] positive. In addition, the time since the previous administration of IMP will be reported (in days).

A study participant will be considered

- Overall [REDACTED] Positive if having at least one scheduled assessment that is confirmed positive during the treatment period (ie, classifications (2) to (6)).
- Overall [REDACTED] Negative if having no scheduled assessments that are confirmed positive at any time in the treatment period (ie, classification (1)).

Number and percentage of [REDACTED] positive and negative participants at the time of each scheduled assessment and overall will be summarized based on the SS.

The first occurrence of treatment-induced [REDACTED] positivity (based on the definitions above) will be summarized (number and percentage of participants) at each post-Baseline scheduled assessment, based on the SS. This tabulation will count the number of participants at each post-Baseline visit who fulfill at least one of the above defined criteria for treatment-induced positivity; participants will be counted in the numerator based on the earliest visit at which one of these criteria is fulfilled. At other visits, participants will be counted in the denominator (assuming a measurement is available). For all tabulations, percentages will be based on the number of observations at each visit.

The [REDACTED] status by the six categories, defined above, will be tabulated by treatment group, with an additional category "total treatment induced" combining participants who are pre [REDACTED] negative- treatment induced [REDACTED] positive, participants with a missing pre-treatment sample (either missing or insufficient volume) at baseline with one or more [REDACTED] positive post-treatment samples and participants pre [REDACTED] positive- treatment boosted [REDACTED] positive.

The prevalence of immunogenicity, defined as (cumulative) proportion of participants having positive immunodepletion [REDACTED] samples at any point up to and including that time point will be summarized by treatment group based on the SS. Missing samples will not be included in the denominator.

Individual plots of rozanolixizumab concentrations and [REDACTED] titer results as well as [REDACTED] titer results and percentage change from baseline in Total IgG by the six [REDACTED] classes described above will be presented. Spaghetti plots of [REDACTED] titer versus time will be presented for all [REDACTED] positive participants based on the SS.

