## **8.4 PEOT and Final Visit**

All subjects who withdraw early from the Treatment Period should attend a PEOT Visit which will be scheduled as close as possible to the date of the decision for the study or treatment withdrawal.

Subjects are encouraged to complete all visits of the Observation Period following the PEOT Visit by either coming to the clinic or as home nursing visits, if appropriate.

In case a subject is not willing to attend the visits in the Observation Period, the subject should still be strongly encouraged to attend at least the PEOT Visit and the FV.

The FV should be scheduled 12 weeks after their final dose of IMP.

The assessments to be done at the PEOT Visit and the FV are the same as those at Visit 17 and Visit 21, respectively.

In the event a subject enters the OLE immediately after Visit 17, Visit 17 will be the final study visit and there will be no FV.

In the event a subject experiences a relapse, the subject will be stabilized; stabilization visits will be conducted from the time of relapse. Stabilization duration may range from 2 weeks to 12 weeks after the time of relapse. Once stabilized, the subject will continue SOC onwards. Subjects not entering the OLE following stabilization should perform the FV after minimum 12 weeks or maximum 24 weeks post last IMP dose. Management of the stabilization period is summarized in [Table 8-1](#).

After the end of the study, the subjects not entering the OLE study should resume treatment according to their standard care as per the recommendation of their physician.

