### **2.2.3 Immunological variables**

The immunological variables are:

- Values and change from Baseline in serum immunoglobulin concentrations (total IgA, IgE, and IgM) at each scheduled assessment during Treatment and Observation Periods
- Values and change from Baseline in serum complement levels (C3 and C4) and plasma complement levels (C3a and C5a) at each scheduled assessment during Treatment Period
- [REDACTED] status (negative or confirmed positive) and the confirmed positive titer at each scheduled assessment during Treatment and Observation Periods
- Values and change from Baseline in cytokines at each scheduled assessment during Treatment and Observation Periods
- Change in CIDP-specific auto-antibody levels in serum from Baseline during Treatment and Observation Periods (This variable is not in scope of this analysis and reported separately.)
- Values and change from Baseline in [REDACTED] during Treatment and Observation Periods

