### 2.3 Study design and conduct

This is a Phase 2A, multicenter, randomized, subject-blind, investigator-blind, placebo-controlled, parallel-group study evaluating the efficacy, safety, and tolerability of rozanolixizumab for treatment of subjects with CIDP. Eligible subjects will be adults who have a confirmed diagnosis of definite or probable CIDP according to the European Federation of Neurological Societies (EFNS)/ Peripheral Nerve Society (PNS) criteria for CIDP, have been shown to be dependent on treatment with immunoglobulin and who have remained on a stable dosing regimen of immunoglobulin therapy for at least 4 months prior to Screening.

- Treatment Arm 1: rozanolixizumab [REDACTED]  
[REDACTED]
- Treatment Arm 2: placebo sc [REDACTED]  
[REDACTED]

Subjects will be randomized in a ratio of 1:1 to the 2 treatment arms. The randomization will take place on the day of first treatment with investigational medicinal product (IMP). The randomization will be stratified according to previous route of administration for Ig treatment (ie, subcutaneous immunoglobulin (SCIg) and intravenous immunoglobulin (IVIg)).

The dose level of [REDACTED] may be reduced to [REDACTED] (or equivalent placebo) for an individual subject based on their tolerability.

The study consists of:

- Screening Period of between 2 and 5 weeks duration
- The 11-week Treatment Period
- The 12-week Observation Period (from 1 week up to maximum 24 weeks):
  - All subjects completing the Treatment Period (ie, all visits up to Visit 17 performed without a CIDP relapse) will be offered the possibility to enter in the Open-Label Extension (OLE) study, CIDP04, and be treated with rozanolixizumab. If they enter in the OLE, Visit 17 will be the last study visit. The Observation Period will be limited to 1 week for these subjects.

In all other instances the subjects will perform Visits 18 to 21 for efficacy and for safety assessments. Subjects will either return to the clinic/hospital, or, if possible and agreed by both investigator and subject, have home visits conducted by certified healthcare professionals for Visits 18 and 20.

---

- For subjects who complete the Treatment Period without relapse but choose not to enter the OLE directly and wish to first test whether they still need treatment, they will continue the Observation Period without standard of care treatment.

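### SAP 9.3.2: the cumulative immunogenicity prevalence, read literally, keeps earlier positives in the numerator but drops people without a current sample from the denominator, so it can rise with no new positive

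*SAP*

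**What the plan says.** SAP 9.3.2 (heading redacted) describes prevalence of immunogenicity as a cumulative proportion of participants with positive immunodepletion "samples at any point up to and including that time point will be summarized by treatment group based on the SS". Nothing in that definition requires a sample at the time point itself. The paragraph closes with its own denominator rule: "Missing samples will not be included in the denominator".

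Earlier in the section, at the end of the paragraph on first occurrence of treatment-induced positivity, is a general rule: "For all tabulations, percentages will be based on the number of observations at each visit".

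Three further statements fix the time points and who is present at them:

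- SAP 2.2.3 lists the variable as "status (negative or confirmed positive) and the confirmed positive titer at each scheduled assessment during Treatment and Observation Periods", so the Observation Period is covered.
- SAP 9.3.2 treats the Final Visit (FV) as a sampling point. Class 2, for example, covers participants negative at Baseline and "antibody positive at any sampling point post treatment (including FV").
- SAP 2.3 says of participants who complete treatment without relapse: "If they enter in the OLE, Visit 17 will be the last study visit". Protocol 8.4 says the same of immediate OLE entry: "Visit 17 will be the final study visit and there will be no FV".

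The section also sets six participant status classes. Class 5 takes Baseline-positive participants who "are positive at any sampling point post treatment (including FV) with increased titer values compared to baseline". Class 4 takes those positive at any post-treatment point with titers of Baseline magnitude. No order of precedence between the two is stated.

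**The concern.** A cumulative numerator can only stay level or grow. A denominator made up of people sampled at the current visit shrinks whenever someone has left or missed a sample. From that point the two no longer describe the same people, and the ratio is not a proportion of any defined group.

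The loss is part of the design. A participant who completes treatment without relapse and goes straight into the OLE gives a last sample at Visit 17 and none at the Final Visit. Early discontinuation and missed visits have the same effect at earlier time points, less strongly.

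What is at stake is the reading of the exploratory immunogenicity objective (Protocol 3.3, SAP 2.1.3), which concerns incidence and emergence. In arms of about 17, a percentage that climbs at the end of the study could be taken as late emergence when it reflects only who was still there to be sampled.

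**Working it through.** **Plan figures.** The documents state no prevalence figure, so there is none to reproduce. The arm size comes from SAP 2.4: 15 evaluable per group, 10% not usable. 2 × 15 / (1 − 0.10) = 33.3, rounded up to 34. With 1:1 allocation, 34 / 2 = 17 per arm. This agrees with the planned 34.

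**Notation.** Let k be the number ever positive up to the time point, n the number with at least one sample up to it, and m the number sampled at that visit (m ≤ n).

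- Literal SAP rule: k / m.
- Matched rule: k / n.
- Inflation factor: (k / m) / (k / n) = n / m.

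The literal figure is therefore too high whenever k ≥ 1 and m < n, whichever participants are missing. It exceeds 100% only when k > m, that is, when at least n − k + 1 participants have no sample.

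**Illustration.** The values of k and m are assumed, with n = 17 and everyone sampled at least once. There is no new positive after Visit 17 in any cell.

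| Ever positive (k) | Matched k/17 | Literal, 13 sampled | 9 sampled | 6 sampled | 4 sampled | Leavers needed to pass 100% |
|---|---|---|---|---|---|---|
| 4 | 23.5% | 31% | 44% | 67% | 100% | 14 |
| 5 | 29.4% | 38% | 56% | 83% | 125% | 13 |
| 6 | 35.3% | 46% | 67% | 100% | 150% | 12 |
| 10 | 58.8% | 77% | 111% | 167% | 250% | 8 |

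With 5 ever positive and 7 sampled (10 leavers), the literal rule gives 5/7 = 71.4% against 5/17 = 29.4%, a factor of 17/7 = 2.4.

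**If the numerator were also limited to people sampled at the visit.** Take k = 6 and 13 leavers, so 4 are sampled. Between 2 and 6 of the leavers must have been positive. The figure is then (6 − 2)/4 = 100% at one end and (6 − 6)/4 = 0% at the other. It cannot pass 100%, but it is no longer cumulative and can fall over time, which contradicts the SAP's definition.

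**Which visit is affected.** Protocol 8.3.1 and 8.3.2 carry a redacted sample line at Visit 17 and at Visit 21, and none at Visits 18 to 20. That this line is the immunogenicity assay is an inference. Sampling at the Final Visit does not depend on it, because SAP 9.3.2 states it.

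**The case against.** The best counter-argument is that the visit-specific denominator is inferred. The sentence on missing samples does not say at which visit they are missing. It sits in a paragraph with its own cumulative wording and its own population. It could mean participants never sampled up to that point, and then numerator and denominator match and nothing exceeds 100%. The rule about observations at each visit closes a different paragraph. It cannot be wholly universal, since the six-class table has no visit.

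This stands in part: the benign reading is possible. But the SAP does not state it, and it conflicts with a sentence that says it applies to all tabulations. A programmer following the text would have reason to use the visit count.

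A reader might go further in three ways that the documents do not support.

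- **That the Final Visit prevalence is the main immunogenicity result.** The SAP gives it no such status. The six-class table, first occurrence by visit and overall positive or negative status address the same objective, and all available sample results are listed.
- **That the arms cannot be compared, because OLE entry depends on not relapsing.** Departure rates may differ by arm, but the SAP plans only a descriptive summary by group, with no between-arm comparison of prevalence.
- **That one participant is counted in both class 4 and class 5.** Both definitions do fit a Baseline-positive participant with one Baseline-like and one raised titer. However, the same section makes any post-Baseline titer with the predefined fold increase treatment-induced, and counts the boosted class in the treatment-induced total. That points to class 5. What is missing is a sentence of precedence.

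**Conclusion.** The point holds as a wording defect that yields a wrong percentage if followed literally. Its direction does not depend on the assumed counts: one ever-positive participant and one missing sample are enough. Its size does. The inflation is n/m, which the documents do not allow anyone to estimate, and values above 100% need ever-positives to outnumber those sampled.

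The conclusion rests on applying the per-visit rule to this table and on some participants entering the OLE at Visit 17. SAP 3.9.2 expects the last Visit 17 to coincide with the last participant's last visit, which suggests that at least some finish there.

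Consequences are limited. The table is descriptive and exploratory. Primary efficacy does not depend on it, and the prevalence denominator does not enter the participant-level six-class table. It should still be corrected, because the text permits readings with very different results and the correction is cheap.

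**What to change.** In SAP 9.3.2:

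1. Define the prevalence denominator at each time point as Safety Set participants with at least one evaluable sample up to and including that time point. This set never shrinks, though it may grow. If only post-Baseline positivity is intended, restrict both numerator and denominator to post-Baseline samples. Restricting the denominator alone would leave a Baseline-positive participant with no later sample in the numerator only.
2. Exempt this table from the rule that bases percentages on observations at each visit.
3. Show the number sampled at the visit beside each percentage, so that the thinning at the Final Visit is visible.
4. As a minor clarification, state that class 5 takes precedence over class 4 when any post-Baseline titer exceeds the fold limit, in line with the section's treatment-induced rule.

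The cost is a few sentences in the SAP and a small programming change, with no new samples or data.

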### 9.3.3 Serum complement levels and plasma complement levels

Serum (C3 and C4) and plasma (C3a and C5a) complement variables will be listed by treatment group and time point including changes from Baseline. Descriptive summaries will

be presented by treatment group and time point for both absolute values and changes from Baseline.

Any values are that BLQ or ALQ will be handled as described in Section 4.2.4.

### 9.3.4 Cytokines

Serum cytokines will be listed by treatment group and time point, changes from Baseline will be added to the listing. Descriptive summaries will be presented by treatment group and time point for both absolute values and changes from Baseline, both for all participants and for participants experiencing infusion reactions.

Any values are that BLQ or ALQ will be handled as described in Section 4.2.4.

### 9.3.5 CIDP-specific auto-antibodies

CIDP-specific auto-antibody sampling information captured in the eCRF will be listed. No results will be analyzed.

### 9.3.6

will be listed by treatment group and time point. Descriptive summaries will be presented by treatment group and time point for both absolute values and changes from Baseline.

Any values are that BLQ or ALQ will be handled as described in Section 4.2.4.

## 10 SAFETY ANALYSES

All safety analyses will be presented using the SS Listings will be presented by treatment group and participant; tabulations will be presented by visit/timepoint (if applicable) and treatment group.

## 10.1 Extent of exposure

Eligible participants will be randomized 1:1 to receive rozanolixizumab [REDACTED] or placebo. Randomized (intended) dose will be calculated based on participant's weight at screening as follows:

Randomized dose (mg)= weight at screening (kg)\*

The IMP solution contains [REDACTED] of rozanolixizumab. Actual dose in mg at Visit(i) will be calculated as follows:

Actual dose at Visit(i) (mg) = Total actual volume delivered at Visit(i) (mL) \* [REDACTED]  
where actual volume delivered is collected in eCRF, and in case of interruption it should be  
calculated as the sum of actual volumes delivered.

Overall exposure (%) will be calculated as mean exposure (%) at each visit as follows:

Overall exposure (%) =mean([Actual dose at Visit (i) (mg)/ Randomized dose (mg) - 1]\*100)

Overall exposure will be categorized as follows:

- $<-10\%$
- $\geq -10\%$  and  $\leq +10\%$
- $\geq +10\%$

The exposure categories will be used for the definition of the MFAS (Section 3.5.5) as well as for the representation of Pharmacokinetic data (Section 9.1).

## 10.2 Adverse events

Adverse events will be recorded from the time of informed consent until study completion. All AEs will be coded (Section 3.8) and categorized by relationship to rozanolixizumab.

In addition, AEs will be classified according to the Common Terminology Criteria for Adverse Events (CTCAE) Version 5.0 for severity. For any AEs where it is not possible to provide a CTCAE grading, the events will be assessed using a standard intensity classification (mild, moderate and severe).

A TEAE is defined as any event that was not present prior the first administration of IMP or any unresolved event already present before the first administration of IMP that worsens in intensity following exposure to treatment until 8 weeks following the last administration of IMP. Adverse events starting before the first administration of IMP or later than 8 weeks after the administration of the last IMP will not be considered TEAEs. Such events will be listed only.

Where dates are missing or partially missing, AEs will be assumed to be treatment-emergent unless evidence exists that does not allow the AE to be treatment-emergent. Handling of missing dates/times for classification of AEs as TEAEs is described in Section 4.2.7.

The following rules will be used to assign a TEAE to the study periods:

1. **Treatment Period:** a TEAE will be assigned to the Treatment Period for the tabulations if the start date/time of the event is at the time of or after the first administration of IMP on Day 1, up to Visit 17/PEOT (non-inclusively).
2. **Observation Period:** a TEAE will be assigned to the Observation Period for the tabulations if the start date/time of the event is at or after Visit 17/PEOT till 8 weeks after administration of the last IMP.
  - The Observation Period's TEAEs will be stratified by TEAEs of participants who received/did not receive standard of care treatment (i.e. Ig treatment) between start of the Observation Period and occurrence of the TEAE.

The number and percentage of participants who experience TEAEs will be summarized by Treatment Period, Observation Period (standard of care treatment status identified by WHODD J06BA01 and J06BA02) and Overall with respective treatment group. The following summaries will be presented:

- Incidence of TEAEs (overview including number and percentage of participants with any TEAEs, serious TEAEs, discontinuations due to TEAEs, related TEAEs, TEAEs with CTCAE Grade 3 and above [or rated as 'severe' for events with no CTCAE classification], and deaths; event counts will also be included)
- Incidence of TEAEs by SOC, HLT and PT
- Incidence of TEAEs during the Dosing Period by SOC, HLT and PT
- Incidence of serious TEAEs by SOC, HLT and PT
- Incidence of non-serious TEAEs by SOC, HLT and PT
- Incidence of AEs of special interest by SOC, HLT and PT
- Incidence of AEs of interest by SOC, HLT and PT

- Incidence of TEAEs by relationship, SOC, HLT and PT
- Incidence of TEAEs by maximum relationship, SOC, HLT and PT
- Incidence of serious TEAEs by relationship, SOC, HLT and PT
- Incidence of non-serious TEAEs by relationship, SOC, HLT and PT
- Incidence of fatal TEAEs by relationship, SOC, HLT and PT
- Incidence of TEAEs by maximum intensity (mild, moderate and severe), SOC, HLT and PT
- Incidence of non-serious TEAEs above threshold of 5% of participants by SOC and PT
- Incidence of non-serious TEAEs above threshold of 5% of participants by relationship, SOC and PT
- Discontinuation due to AEs

Summary tables will contain counts of participants, percentages of participants in parentheses and the number of events. A participant who has multiple events in the same SOC, HLT and PT will be counted only once in the participant counts but all events will be included.

Adverse event summaries will be ordered by alphabetical SOC, alphabetical HLT within SOC and decreasing frequency in the active treatment group.

In summaries including intensity, the CTCAE categories will be summarized according to the following categories:

- Grade 1: Mild
- Grade 2: Moderate
- Grade 3: Severe
- Grade 4: Severe
- Grade 5: Severe
- not gradable

In the case both category types are captured and the mapping to a standard intensity classification per above rule results in a class different from the standard intensity classification given in the eCRF, the worst case will be used.

These will be tabulated together with the AEs that were not classified according to CTCAE criteria i.e., all Grade 1 AEs as per CTCAE criteria will be included in the 'mild' category together with those AEs classified as mild as per the 'standard' intensity classification.

A listing will be presented by treatment group and participant for all AEs. This will include the onset date/time and outcome date/time of the event (including relative days), the AE duration, days since first dose of IMP, days since most recent dose of IMP, actual dose received, study period, pattern of event, severity/intensity, relationship, action taken and outcome. In addition, the listing will flag AEs that led to discontinuation, TEAEs, serious adverse events (SAEs), AEs of interest, AEs of special interest and infusion reactions.

AEs of focus (ie, TEAEs that are a review focus for rozanolixizumab or the participant population) will be summarized, in separate tables, detailing all TEAEs meeting the following criteria described below:

- Headache using the UCB-defined search criteria.
- Gastrointestinal disturbances using the UCB-defined search criteria.
- Hypersensitivity reactions using the criteria SMQ='Hypersensitivity'
- Anaphylactic reactions using the criteria SMQ='Anaphylactic reaction' and the UCB-defined search criteria.
- Injection site reactions using the UCB-defined search criteria.
- Infusion reaction collected on the eCRF AE page.
- Opportunistic infections using the UCB-defined search criteria.
- Reductions in albumin and plasma proteins using the UCB-defined search criteria.
- Effects on the kidney using the criteria SMQ='Acute renal failure'
- Drug related hepatic disorders using the criteria SMQ='Drug related hepatic disorders - comprehensive search'.

For each of the above-mentioned AEs of focus the following summaries will be presented:

- Incidence of all AEoFs by SOC, HLT and PT
- Incidence of all AEoFs by Relationship, SOC, HLT and PT
- Incidence of all serious AEoFs by SOC, HLT and PT
- Incidence of all AEoFs by Maximum Intensity, SOC, HLT and PT

UCB definitions for AEoF are found in a separate document "Adverse Events (AEs) of Focus for the rozanolixizumab Program" version 1.3, dated 04 Aug 2020.

